6.3 Randomization and Blinding

Upon presentation at the emergency department, patients will be clinically judged for in- and exclusion criteria, among which indication for hospitalization. When eligible the patient will be notified about the study. When the patient is interested in participating, the patient information form will be discussed by the treating physician. The participation being voluntarily and the opportunity to discontinue participation will be made clear by the treating physician. Informed consent will be requested with at least two hours of time to decide. Randomisation will occur by a computer-based program. We will use a block-randomisation with randomly alternating blocks of 4 and 6 patients and with stratification by center. The outcome assessors at day 30 will be blinded for the treatment arm. Two independent physicians will be selected per center to be the outcome assessors. The patient will also be blinded for the treatment strategy (usual care or PCT-guided), but not for the received treatment (antibiotics or no antibiotics next to prednisolone).

6.4 Study Assessments

Visit	Baseline	Day 3	Day 5	Day 10	Day 30
Informed consent	x				
Medication history	x				
Vital signs	x				
Check for eligibility	x				
Sputum collection	x				
Blood sampling, including procalcitonin*	x				
Blood samples for CRP, eosinophils	x	x	x		
Serum for storage	x				
Sputum for storage	x				
Modified Anthonisen criteria	x	x	x	x	x
Clinical assessment for treatment failure		x	x	x	x
CAT	x			x	x
EXACT-RS	x			x	x
EQ-5D-5L + resp. bolt-on	x			x	x
iMCQ (adapted version)					x
Randomization	x				
Antibiotic consumption	x	x	x	x	x
Prednisolone consumption	x	x	x	x	x
Diary cards according to modified	x	x	x	x	x

Anthonisen criteria					
Assesment of adverse effects/events	x	x	x	x	x

* (PCT will only be reported for the randomised PCT group and not for the usual care group during the study period. The measurement will be performed in the usual care group but this will be blinded until the study ends.)

Analysis Time Windows

Visit (target day)	Lower bound (days)	Upper bound (days)
Baseline (0)	N/A	N/A
Day 3	N/A	N/A
Day 5	N/A	N/A
Day 10	9	11
Day 30	28	32

This section will go beyond the description of variables provided in the protocol in that it will list and describe all important study variables from a statistical perspective. The description of each variable should include:

- Modified Anthonisen criteria
 - Items are measured on with 3 optional answers where the first option = no deterioration, the second is slightly worse and the third option = much worse.
- EXACT respiratory symptoms questionnaire
 - Comprised of 11 questions about respiratory symptoms common for patients with COPD
 - Items are measured on a 0-3 or 0-4 ordered categorical scale for which a 0 = not at all, 1 = slightly or rarely or a little (depending on the question), 2 =moderately, 3 = severely or quite a bit, and 4 = extremely
 - The answer scales slightly differ depending on the question, for example breathlessness is scored on 0-3 ordered categorical scale for which a 0 = unaware of breathlessness, 1 = breathless during strenuous activity, 2= breathless during light activity, 3= breathless when washing or dressing, or present when resting
- COPD assessment test (CAT)
 - Comprised of 8 items to assess the impact of COPD on patients quality of life.
 - Items are measured on a 0-5 ordered categorical scale for which 0 = never experience this symptom to 5 = experience this symptom continuously

7 Sample Size

In international literature there is scarce information about the percentages of treatment failure in patients admitted with an AECOPD receiving usual care. Therefore, we have performed a further search on PCT studies with a primary outcome of 30-day treatment failure. In the study by Schuetz et al. [6], who studied patients with lower respiratory tract infection, 30-day treatment failure was observed in 15.5% of the patients randomised to biomarker-based treatment, as compared to 18.9% in those randomised to usual care. This implies a relative risk of 0.82 in favour of the biomarker-based strategy. The study by Schuetz et al. was designed as a non-inferiority study, using a non-inferiority boundary of 7.5%. In view of these data we decided to design our study as a non-inferior study, whereas we choose a non-inferiority boundary of 5.0%. We based the primary outcome on the study of Huang et al. [13]. The incidence of the primary outcome was 20.4%. Using the relative risk of 0.82 in favour of the PCT-guided treatment group we expect the incidence of the primary outcome to be 16.7% in the PCT-guided treatment group. Then a total sample size of 626 is required (313 per treatment arm) to demonstrate non-inferiority with a power of 80%, and applying a one-sided alpha error of 0.025. We aim to enroll a total of 690 patients, accounting for a 10% drop-out rate.

8 General Analysis Considerations

8.1 Timing of Analyses

Give details here of when, or under what criteria, the final analyses will be performed. Give details of what data cleaning and locking processes must take place to comply with standard operating procedure (SOP) specifications. For example:

- The final analysis will be performed when 693 subjects have completed the follow-up of 30 days, after which the database will be locked.

8.2 Analysis Populations

(ICH E3; 9.7.1, 11.4.2.5. ICH E9; 5.2)

8.2.1 Full Analysis Population (or Intention to Treat or Modified Intention to Treat)

- All subjects who were randomized and who took at least one dose of study drug.

8.2.2 Per Protocol Population

- All subjects who:
 - met all inclusion/exclusion criteria,
 - attained a sufficient compliance to the treatment received, treatment with prednisolone and/or antibiotics, when prescribed on admission for at least 5 days,
 - did not present serious deviations from the protocol.

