### **10. STATISTICAL ANALYSIS**

There will be two analysis populations for this study:

1. The Intention-to-Treat (ITT) population is defined as all randomised patients who took at least one dose of study drug.
2. The Per-Protocol (PP) population is defined as a subset of ITT population constituted by those patients who: a) met all inclusion/exclusion criteria, b) attained a sufficient compliance to the treatment received, treatment with prednisolone and/or antibiotics, when prescribed on admission for at least 5 days, and c) did not present serious deviations from the protocol.

The analysis of all the efficacy variables will be performed on both the ITT and the PP populations in order to assess the robustness of the findings from the ITT population. All the demographic and baseline patients' characteristics and safety outcomes will be analysed using the ITT population.

All efficacy variables will be analysed for ITT and the PPS, and the PP population will be considered the primary population for assessing efficacy.

---

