5.2 Endpoints

The primary objective of this study is to show that at hospitalization for a severe exacerbation of COPD, PCT-guided treatment regarding antibiotic use is non-inferior to usual care consisting of prednisolone and or antibiotics, in terms of treatment failure at day 30 for patients hospitalized because of an acute exacerbation of COPD (AECOPD). Treatment failure is defined as disease-related mortality, endotracheal intubation, vasopressors, renal failure, lung abscess/empyema, pneumonia development or hospital readmission within 30 days after inclusion of the study.

The secondary objectives of this study are to assess the following secondary endpoints:

- Treatment failure defined as an incomplete resolution of the clinical signs and symptoms associated with the AECOPD at day 30 after inclusion of the study (i.e not reaching the baseline condition prior to the AECOPD) scored using the modified Anthonisen criteria.
- Change in Quality of Life on day 1, 10, and after 30 days using the COPD Assessment Test (CAT)
- EXACT – Respiratory symptoms scale (at admission, at day 10 and at day 30 after admission)
- Time to complete resolution of symptoms according to daily symptom diaries evaluating the modified Anthonisen criteria
- Start of antibiotic therapy after an initial opposite decision (after 48 hours)
- Non-Invasive ventilation after 72 hours of admission
- Length of hospitalization
- Re-exacerbation within 30 days
- Side effects (gastro-intestinal complaints, allergic reactions)
- Cumulative antibiotic consumption
- Cumulative prednisolone consumption

6 Study Methods

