6.1 General Study Design and Plan

- Study design: prospective, randomized-controlled trial. Patients will be randomized to biomarker-guided treatment (based on blood procalcitonin level) or to usual care. In the usual care arm, and in the biomarker guided-arm in case of high ($> 0.25\mu\text{g/L}$) procalcitonin, patients will receive amoxicillin-clavulanic acid.
- Type of Comparison: non-inferiority.
- Type of control(s): usual care
- Level and method of blinding (e.g. double-blind): The patient and the outcome assessor will be blinded for the allocated treatment strategy. Two independent physicians will be selected per center to be the outcome assessors. The patient will not be blinded for the treatment itself (prednisolone with or without antibiotic therapy).
- Method of treatment assignment: We will use a block-randomisation with randomly alternating blocks of 4 and 6 patients (random permuted block randomisation). The randomisation will be stratified per center.
- At what point in time subjects are randomized relative to treatments, events and study periods: Upon presentation at the emergency department, patients will be clinically

judged for in- and exclusion criteria, among which indication for hospitalization. When eligible the patient will be notified about the study. When the patient is interested in participating, the patient information form will be discussed by the treating physician. The participation being voluntarily and the opportunity to discontinue participation will be made clear by the treating physician. Informed consent will be requested with at least two hours of time to decide

- Sequence and duration of all study periods: screening will occur on the first day of admission as described above, baseline characteristics will be collected within 24 hours of admission, active treatment will be 5 days, follow-up will be 30 days.

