8.2.3 Safety Population

- All subjects who received any study treatment (including control) but excluding subjects who drop out prior to receiving any treatment.

The analysis of all the efficacy variables will be performed on both the ITT and the PP populations in order to assess the robustness of the findings from the ITT population.

All the demographic and baseline patients' characteristics and safety outcomes will be analysed using the ITT population.

All efficacy variables will be analysed for ITT and the PPS, and the PP population will be considered the primary population for assessing efficacy.

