The quality of life endpoints, using the COPD Assessment Test (CAT) and the EXACT-respiratory symptoms questionnaire, consist of multiple (three) measurements per subject. These measurements are all performed on the same time point (baseline, day 10 and day 30). These endpoints will be scored using the mean score and standard deviation when normally distributed and a median with the inter quartile range when the data have a skewed distribution. These data will be analyzed with a mixed effects model with random effects for center and patient to account for the extra hierarchical level in the data. The residuals will be evaluated for normality to test the assumptions of the models. In case of violations, transformations will be conducted on the dependent variable.

The unpaired continuous variables will be reported using the mean score and the standard deviation (normal distribution) or the median with the inter quartile range (skewed distribution). These variables will be analyzed using an mixed effects model.

The frequency and percentage will be reported for the categorical (mostly dichotomous) variables. Analysis of these variables will be performed using a logistic mixed-effects model.

- The analysis populations upon which the tables and figures will be based will be the per-protocol analysis population.

Table 2. Primary endpoint and secondary endpoints

	PCT-guided treatment (n = 315)	Usual care (n = 315)		p-value
Primary endpoint:				
Overall treatment failure:	n (%)	n (%)	OR (95% CI)	
- Disease-related mortality	n (%)	n (%)		
- Endotracheal intubation	n (%)	n (%)		
- Vasopressors	n (%)	n (%)		
- Renal failure	n (%)	n (%)		
- Lung abscess/empyema	n (%)	n (%)		
- Pneumonia development	n (%)	n (%)		
- Hospital readmission	n (%)	n (%)		
Secondary endpoints				
Incomplete resolution of the clinical signs and symptoms at day 30 after (scored using the modified Anthonisen criteria)	n (%)	n (%)	OR (95% CI)	

Change in QoL using the CAT: after 10 days after 30 days	mean (SD)or median [IQR]	mean (SD)or median [IQR]		
Start of antibiotic therapy after an initial opposite decision (after 48 hours)	n (%)	n (%)	OR (95% CI)	
Side effects (gastro-intestinal complaints, allergic reactions)	n (%)	n (%)	OR (95% CI)	
Cumulative antibiotic consumption	mean/median days (SD) or [IQR]	mean/median days (SD) or [IQR]		
Cumulative prednisolone consumption	mean/median days (SD) or [IQR]	mean/median days (SD) or [IQR]		

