10.2 Secondary Efficacy Analyses

10.2.1 Secondary Analyses of Primary Efficacy Endpoint

Our primary analysis population will be the per-protocol population because of the non-inferiority design. The secondary analysis population will be the intention-to-treat analysis.

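### The 5-day compliance rule for the primary per-protocol set has no exception for patients whose treatment ends early because they died or reached the endpoint

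*SAP*

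**What the plan says.** **PP rule.** SAP 8.2.2 requires that the patient "attained a sufficient compliance to the treatment received, treatment with prednisolone and/or antibiotics, when prescribed on admission for at least 5 days". Protocol section 10 has the same clause ("attained a sufficient compliance to the treatment received"). Neither sets a threshold for what is sufficient, and neither mentions patients who stop because of death or an endpoint event.

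**Role of PP.** SAP 8.2.3 states that "the PP population will be considered the primary population for assessing efficacy", and SAP section 9 that "The analysis populations upon which the tables and figures will be based will be the per-protocol analysis population". In SAP 10.2.1, "The secondary analysis population will be the intention-to-treat analysis". Both populations are to be analysed for every efficacy variable, but no rule requires them to agree before non-inferiority is declared.

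**Endpoint window.** SAP 5.2: "Treatment failure is defined as disease-related mortality, endotracheal intubation, vasopressors, renal failure, lung abscess/empyema, pneumonia development or hospital readmission within 30 days" of inclusion. In the SAP 6.4 schedule the row "Clinical assessment for treatment failure" is marked for days 3, 5, 10 and 30. SAP 6.1 gives the periods: "active treatment will be 5 days, follow-up will be 30 days".

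**Related text.**
- SAP 8.4 and protocol 8.4 expect most investigator withdrawals to be treatment failures. The PP definition does not use this.
- SAP 9.3 removes from PP a patient who is given antibiotics despite a procalcitonin at or below the cut-off. It sets no time limit and makes no exception for antibiotics begun after an endpoint event. It also discusses early termination of antibiotics without saying whether that patient leaves PP.
- Protocol 4.3 and SAP 6.2 exclude patients with an indication for ICU or non-invasive ventilation within 72 hours of admission, and PP requires every eligibility criterion to be met.

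**The concern.** The compliance window (days 1 to 5) lies inside the endpoint window (inclusion to day 30), and the plan itself schedules failure assessments on days 3 and 5. If compliance means five days of treatment taken, a patient who dies on day 2 cannot comply and drops out of the set on which non-inferiority is declared. Any other early failure that stops treatment does the same. Membership of the primary population then depends on the outcome it is meant to measure.

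The SAP 9.3 rule can act on one arm only, because only the PCT arm has a procalcitonin-based instruction to deviate from. SAP 8.5.1 names the feared harm: a patient with a falsely low procalcitonin deteriorates without antibiotics. If that patient develops pneumonia and is then treated with antibiotics, the failure can be removed from the arm in which it occurred.

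In a non-inferiority comparison, removing failures from both arms shrinks a true excess, and removing more of them from the PCT arm shrinks it further. Both favour a false conclusion of non-inferiority.

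**Working it through.** **Inputs from the documents** (SAP section 7 and 8.5.5; protocol 4.4 and 10.4): usual-care failure 20.4%; expected PCT-arm failure 16.7%; margin δ = 5.0 points absolute; power 80%; one-sided α 0.025, or 0.0492/2 = 0.0246 at the final analysis; 315 per arm after drop-out.

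**Input not in the documents:** the share *f* of failures that occur before day 5 and are removed. It is assumed, from 5% to 30%, equal or unequal between arms.

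**Step 1: reproduce the plan's sample size.**
n per arm = (z₁₋α + z₁₋β)² × [p₁(1−p₁) + p₂(1−p₂)] / (δ − (p₁ − p₂))²
- α = 0.025: (1.960 + 0.842)² × (0.1391 + 0.1624) / (0.05 + 0.037)² = 7.849 × 0.3015 / 0.007569 = 312.6, so 313 per arm and 626 in total. This matches.
- α = 0.0246: 7.887 × 0.3015 / 0.007569 = 314.2, so 315 per arm. This matches.

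**Step 2: effect of removing early failures.**
Observed PP rate = p(1−f)/(1−pf); PP size per arm = 315(1−pf).
P(conclude non-inferiority) = Φ[(δ − d)/SE − z₁₋α], with d the PP difference, SE unpooled and α = 0.0246.

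The true rates are set at the margin: 20.4% usual care and 20.4 + 5.0 = 25.4% PCT. Only early failures are removed.

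**Step 3: one case in full, f = 20% in both arms.**
- PCT: 0.254 × 0.8 / (1 − 0.0508) = 0.2141, n = 299.0
- Usual care: 0.204 × 0.8 / (1 − 0.0408) = 0.1701, n = 302.1
- d = 0.0439; SE = √(0.2141 × 0.7859/299.0 + 0.1701 × 0.8299/302.1) = 0.0321
- Φ[(0.05 − 0.0439)/0.0321 − 1.967] = Φ(−1.778) = 3.8%

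**Step 4: range.** Differences are taken from unrounded rates.

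| Failures removed, PCT / usual care | Patients lost, PCT / usual care | PP rates | PP difference (points) | One-sided error |
|---|---|---|---|---|
| 0% / 0% | 0 / 0 | 25.4% v 20.4% | 5.0 | 2.46% |
| 5% / 5% | 4.0 / 3.2 | 24.4% v 19.6% | 4.9 | 2.7% |
| 10% / 10% | 8.0 / 6.4 | 23.5% v 18.7% | 4.7 | 3.0% |
| 20% / 20% | 16.0 / 12.9 | 21.4% v 17.0% | 4.4 | 3.8% |
| 30% / 30% | 24.0 / 19.3 | 19.2% v 15.2% | 4.0 | 4.9% |
| 20% / 10% | 16.0 / 6.4 | 21.4% v 18.7% | 2.7 | 10.6% |
| 10% / 0% | 8.0 / 0 | 23.5% v 20.4% | 3.1 | 8.4% |
| 20% / 0% | 16.0 / 0 | 21.4% v 20.4% | 1.0 | 22.6% |
| 0% / 10% | 0 / 6.4 | 25.4% v 18.7% | 6.7 | 0.7% |

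**Step 5: power.** At the design rates (16.7% v 20.4%), equal removal of 5% to 30% leaves power between 79.7% and 79.9%, against 80.1% with no removal. The sample size is not affected; the validity of the conclusion is.

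The calculation uses the absolute 5-point margin on the risk difference, as in the protocol and the sample size. SAP section 9 and 10.1 judge non-inferiority on an odds ratio; that scale was not computed.

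**The case against.** **The wording does not force the loss.** *Sufficient* has no threshold, and the 5 days can attach to the prescription instead of to the days taken. On that second reading, a patient who followed a 5-day prescription until death on day 2 was compliant and stays in PP. This stands, so exclusion is a risk left open by the text and not a certainty. It also means that membership could be settled case by case after outcomes are known.

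**Most endpoint components do not end treatment.** A reader might infer that every early failure falls out of PP. The documents do not support that. Intubation, vasopressors, renal failure, abscess or empyema, and pneumonia do not in themselves stop prednisolone or antibiotics, and readmission needs a prior discharge. Only death necessarily stops treatment. Likewise, a change of treatment after deterioration is not an endpoint component, so such a patient is a lost failure only if a listed event also occurs.

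**SAP 9.3 may concern only the decision on admission.** That is possible, but the section does not say so. The plan also expects later starts: beginning antibiotics after an initial decision against them is a secondary endpoint.

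**The direction is not fixed.** Loss confined to usual care is conservative (0.7% in the table). This stands.

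**ITT is analysed too.** A discrepancy would be visible there, which helps. But ITT is secondary and no agreement rule exists, so an adverse ITT result would not formally block the claim.

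**Conclusion.** The point holds as a gap in the definition of the primary population. Read as five days taken, the rule removes deaths before day 5 and any other early failure that stops treatment. SAP 9.3 can remove further failures from the PCT arm alone.

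The size cannot be determined from the documents, because they give no timing of failures. With equal loss the inflation is modest: 2.7% to 4.9% for assumed shares of 5% to 30%, and close to none if few failures are early. Unequal loss is the more serious case: about 10.6% for 20% against 10%, and more if the loss is confined to the PCT arm. These figures are illustrations at the margin under a normal approximation, not predictions.

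It would go too far to say that early failures cannot meet the rule, or that the bias always favours the PCT arm. The defect is still worth correcting, because this set carries the confirmatory decision and the correction is small.

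**What to change.** The changes concern the analysis population only.

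1. **SAP 8.2.2 and protocol 10:** compliance is assessed only up to the first primary endpoint event, death or day 5, whichever comes first. An otherwise eligible patient with an earlier endpoint event stays in PP and counts as a failure.
2. **SAP 9.3:** antibiotics started after a primary endpoint event are not a PP deviation.
3. **PP eligibility limb:** the criterion on ICU or non-invasive ventilation within 72 hours is judged, for PP membership, on the patient's status at randomisation. Otherwise it could remove early failures by another route.

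Two additions would help: a numerical definition of sufficient compliance, and a statement that PP and ITT must both support non-inferiority.

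Separately, protocol section 5 leaves antibiotic duration in usual care to the physician, while SAP 9.3 expects five days in both groups. These passages must be reconciled, because the 5-day rule could otherwise exclude usual-care patients who followed the protocol.

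**Cost:** a few sentences in SAP 8.2.2, SAP 9.3 and protocol 10. Treatment, visits and sample size do not change. The rule needs the dates of the first endpoint event and of any later antibiotic start, so the sponsor should confirm that the eCRF records them. The text should be settled before the interim analysis or, if that has passed, before anyone deciding PP membership sees outcomes by arm.

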8.2.3 Safety Population

- All subjects who received any study treatment (including control) but excluding subjects who drop out prior to receiving any treatment.

The analysis of all the efficacy variables will be performed on both the ITT and the PP populations in order to assess the robustness of the findings from the ITT population.

All the demographic and baseline patients' characteristics and safety outcomes will be analysed using the ITT population.

All efficacy variables will be analysed for ITT and the PPS, and the PP population will be considered the primary population for assessing efficacy.

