5.1 Study Objectives

We hypothesize that at hospitalization for a severe acute exacerbation for COPD, biomarker-guided treatment based on procalcitonin level to guide antibiotic administration is non-inferior to usual care consisting of prednisolone and or antibiotics, which is based on a clinical decision, in terms of treatment failure at day 30.

The secondary objectives are to establish that a biomarker-guided decision algorithm results in an improvement in quality of life, a decrease in consumption of antibiotics, and a reduction of important side effects.

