8.5.4 Analysis Methods to Minimize Bias

The per protocol (PP) population is the main analysis population because of the non-inferiority design of the trial.

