9.5 Concurrent Illnesses and Medical Conditions

The summary statistics will be produced in accordance with section 9.

10 Efficacy Analyses

- Summary statistics that will be produced for continuous and categorical data:
 - The quality of life endpoints, using the COPD Assessment Test (CAT) and the EXACT-respiratory symptoms questionnaire, consist of multiple (three) measurements per subject. These measurements are all performed on the same time point (baseline, day 10 and day 30). These endpoints will be scored using the mean score and standard deviation when normally distributed and a median with the inter quartile range when the data have a skewed distribution. These data will be analyzed with a mixed effects model with random effects for center and patient to account for the extra hierarchical level in the data. The residuals will be evaluated for normality to test the assumptions of the models. In case of violations, transformations will be conducted on the dependent variable.
 - The unpaired continuous variables will be scored using the mean score and the standard deviation (normal distribution) or the median with the inter quartile range (skewed distribution). These variables will be analyzed using an mixed effects model.
 - The frequency and percentage will be reported for the categorical (mostly dichotomous) variables. Analysis of these variables will be performed using a logistic mixed-effects model.

- Analysis populations that will be used and identification of the primary population.
 - We will analyze the population with a per-protocol analysis and an intention-to-treat analysis. The primary population will be the per-protocol population.

- A statement of the clinical objective rephrased in precise statistical terms (null and alternative hypotheses):
 - Null hypothesis: PCT-guided treatment regarding antibiotic use is inferior to usual care in patients with an acute exacerbation of COPD
 - Alternative hypothesis: PCT-guided treatment regarding antibiotic use is non-inferior to usual care in patients with an acute exacerbation of COPD
- The nature of the hypothesis is confirmatory

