
25. ZonMW. Budget Impact Analyses in de praktijk. Leidraad Budget Impact analyse [Internet]. 2020 Feb. Available from: www.facebook.com/zonmwNL

17 Listing of Tables, Listings and Figures

Tables:

- Table 1:
 - Title: Baseline characteristics
 - 3 columns, at least twelve rows
 - Per-protocol population will be given, since this is the primary analysis population
 - Mean will be reported with one decimal, just as the standard deviation and range
 - Median will be reported with one decimal
 - Frequencies will be reported in rounded numbers
 - Percentages will be reported after the frequency as (%) with one decimal
 - Interquartile range will be reported after the median as [IQR] with one decimal

- Table 2:
 - Title: Primary endpoint and secondary endpoints
 - 5 columns, 14 rows
 - Per-protocol population will be given, since this is the primary analysis population
 - Frequencies will be reported in rounded numbers
 - Percentages will be reported after the frequency as (%) with one decimal
 - Interquartile range will be reported after the median as [IQR] with one decimal
 - Adjusted odds ratio/RR/RD will be reported with 2 decimals
 - 95% C.I. will be reported with 2 decimals
 - P-value will be reported with 3 decimals
 - Mean/median value of the CAT and EXACT will be reported with one decimal, just as the standard deviation or the interquartile range[IQR]

- Table 3:

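### The per-protocol set leads every efficacy endpoint, but its non-inferiority rationale covers only the primary one; antibiotic consumption is the endpoint most clearly biased

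*SAP*

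**What the plan says.** SAP 8.2.3 sets one rule for every efficacy endpoint: "All efficacy variables will be analysed for ITT and the PPS, and the PP population will be considered the primary population for assessing efficacy". The opening of Protocol section 10 carries the same rule. SAP section 10 repeats it ("The primary population will be the per-protocol population"), and SAP section 9 extends it to the outputs: "The analysis populations upon which the tables and figures will be based will be the per-protocol analysis population". SAP section 17 applies it by name to Tables 1 and 2: "Per-protocol population will be given, since this is the primary analysis population".

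The reason appears twice. SAP 8.5.4 says "The per protocol (PP) population is the main analysis population because of the non-inferiority design of the trial", and SAP 10.2.1 says "Our primary analysis population will be the per-protocol population because of the non-inferiority design". No other reason is given.

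The secondary objectives in SAP 5.1, and in Protocol section 2, are to establish that the PCT-guided algorithm "results in an improvement in quality of life, a decrease in consumption of antibiotics, and a reduction of important side effects". SAP 10.2.2 gives no non-inferiority margin for any secondary endpoint.

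PP membership depends partly on conduct after randomisation. SAP 8.2.2 requires sufficient compliance and no serious deviation. SAP 9.3 classes antibiotics prescribed despite low PCT as a major deviation that takes the patient out of PP.

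**The concern.** Leading with PP is a recognised choice for a non-inferiority test, because non-adherence tends to make two strategies look alike and so favours a non-inferiority conclusion. That argument does not carry over to a claim that one strategy is better. There, removing patients after randomisation gives up the protection of randomisation and can create a difference.

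The removal named in SAP 9.3 is also one-sided. In usual care the physician is free to prescribe and PCT is not reported during the study (Protocol section 3; SAP 6.4), so an override of a low PCT cannot occur there. In the PCT arm every patient removed for this reason is an antibiotic user. At stake is the size of the reduction in antibiotic use, a stated objective, as it would appear in the main results table.

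**Working it through.** **Sample size first.** With failure rates of 20.4% and 16.7%, a 5-point margin, one-sided alpha 0.025 and 80% power, n per arm = (1.960 + 0.842)² × (0.204×0.796 + 0.167×0.833) / (0.05 + 0.037)² = 313, or 626 in total, as stated. At a two-sided final level of 0.0492 it is 315, also as stated. Both rest on the primary endpoint, so nothing below changes them.

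**Antibiotic use.** Let e be the share of the PCT arm removed for override. All of these patients received antibiotics, so

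- use in all randomised = (1 − e) × use in PP + e × 1
- use in PP = (use in all randomised − e) / (1 − e)

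This is never above the figure for all randomised patients. For this exclusion, then, the direction follows from the rule itself and needs no assumption about prognosis.

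For the size, let L be the share with low PCT and v the share of those overridden, and assume that all high-PCT patients are treated. Then e = L×v, all-randomised use = (1 − L) + L×v, and PP use = (1 − L)/(1 − L×v). Usual-care use is set at 65%, the national figure in Protocol section 1. The documents do not give L or v, so both are assumptions.

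| L | v | Removed from PCT arm | Use, all randomised | Use, PP | Reduction, all randomised | Reduction, PP |
|---|---|---|---|---|---|---|
| 60% | 10% | 6.0% | 46.0% | 42.6% | 19.0 points | 22.4 points |
| 75% | 20% | 15.0% | 40.0% | 29.4% | 25.0 points | 35.6 points |
| 85% | 30% | 25.5% | 40.5% | 20.1% | 24.5 points | 44.9 points |

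Over L of 60% to 85% and v of 10% to 30%, PP enlarges the reduction by about 3 to 20 points.

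As a limiting case, suppose true use is 65% in both arms. With L = 75%, v = (0.65 − 0.25)/0.75 = 53% and e = 40%, so PP use = 0.25/0.60 = 42%. For L = 60% and 85%, PP use is 53% and 30%. PP would show a reduction that did not occur.

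**CAT.** Assume a fraction f of the PCT arm is removed, those patients improve less by a deficit D, the SD is 7 points (the documents give none), and there is no true effect. Then shift = f×D, SE = 7×√(1/(315(1 − f)) + 1/315), and rejection rate = Φ(−1.96 + shift/SE) + Φ(−1.96 − shift/SE).

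| f | D | Shift | Two-sided rejection at nominal 5% |
|---|---|---|---|
| 5% | 3 | 0.15 | 5.8% |
| 10% | 5 | 0.50 | 14.1% |
| 15% | 5 | 0.75 | 25.2% |

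A simulation of 20,000 trials with 15% removed and those patients 0.5 SD worse gave 14.8% under PP and 4.8% in all randomised patients.

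**The case against.** The strongest reply is that intention-to-treat (ITT) results are planned for every efficacy variable (SAP 8.2.3 and 10), so nothing is hidden. That stands: the fault is confined to which set leads and fills Table 2. The text is also unsettled. Just before naming PP as primary, SAP 8.2.3 speaks of checking the robustness of the ITT findings, as if ITT led.

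A reader might infer more than the documents support in four places.

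- **A false quality-of-life benefit would be established.** Nothing says that overridden patients are sicker. SAP 9.3 raises a different worry, that antibiotics may make them recover. SAP 10.2.2 treats a CAT difference below 2 points as clinically non-significant, and the modelled shift is 0.15 to 0.75 points. With the same inputs, PP would show a PCT advantage of 2 points or more only 0.4% of the time (0.05% to 1.6%).
- **Every secondary endpoint is a stated superiority claim.** Only quality of life, antibiotic consumption and side effects are worded that way. For the others it is inferred from testing without a margin. Side effects are pulled two ways: SAP 8.2.3 puts safety outcomes on ITT, yet they also sit in the PP-based Table 2.
- **A PP-based Table 1 hides the imbalance that exclusions create.** A PP table by arm is where such imbalance would show; an ITT table alone would not show it. What is real is the contradiction: SAP 8.2.3 puts baseline characteristics on ITT, and SAP section 17 puts Table 1 on PP.
- **All PP exclusions push the same way.** Eligibility and compliance exclusions apply to both arms. The SAP does not say clearly whether patients who start antibiotics after 48 hours leave PP, and it does not name untreated high PCT as a deviation. Excluding the latter would pull in the opposite direction.

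**Conclusion.** The point holds, chiefly for antibiotic consumption. A reason that belongs to the primary non-inferiority test has been extended to secondary endpoints that seek a difference. One named exclusion removes antibiotic users from the PCT arm only, so its direction on consumption is known. Its size is not: about 3 to 20 points in the proportion treated, under the assumed ranges for low PCT and override and the national 65%. The SAP measures consumption in days, so these figures illustrate the effect and do not forecast the trial's estimate. For CAT and the other outcomes the bias is possible, with two-sided error of about 6% to 25% under the stated assumptions, but neither direction nor size can be settled from the documents. The primary comparison and its sample size are not affected.

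**What to change.** In SAP 8.2.3, 9, 10 and 17, and in matching wording in Protocol section 10:

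- State that PP leads only the primary non-inferiority comparison.
- State that secondary endpoints are led by all randomised patients analysed as allocated, with PP as a sensitivity analysis, and fill Table 2 accordingly. This set must be defined. The SAP 8.2.1 population requires a dose of study drug, which is an unsuitable condition when the PCT strategy can correctly lead to no antibiotic.
- Report side effects on the ITT basis that SAP 8.2.3 already gives for safety outcomes.
- Reconcile SAP 8.2.3 with section 17 by showing Table 1 for all randomised patients with PP beside it, and reword the sentence in 8.2.3 (and its twin in Protocol section 10) that reads as if ITT led.

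The cost is wording in two documents, so a Protocol change as well as an SAP change, and one redefined analysis set. No additional patients or data collection are needed. The apparent effect on secondary endpoints may be smaller where non-adherence dilutes it.
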